8.4.4 Reporting of Pregnancy

As all participants will be postmenopausal per the medical record, pregnancy is not an anticipated event. However, should a participant become pregnant during the study, she will be allowed to continue in all study activities except MRI assessment.

8.5 Reporting Procedures – Notifying the Study Sponsor

The study clinician will complete a SAE Form within the following timelines:

- All deaths and immediately life-threatening events, whether related or unrelated, will be recorded on the SAE Form and submitted to the data and safety monitoring team/study sponsor within 24 hours of site awareness. See Section 1, Key Roles for contact information.
- Other SAEs regardless of relationship will be submitted to the data and safety monitoring team /study sponsor within 72 hours of site awareness.

All SAEs will be followed until satisfactory resolution or until the site investigator deems the event to be chronic or the adherence to be stable. Other supporting documentation of the event may be requested by the data and safety monitoring team/study sponsor and should be provided as soon as possible.

As a follow-up to the initial report, within the following 48 hours of awareness of the event, the investigator shall provide further information, as applicable, on the unanticipated event or the unanticipated problem in

CONFIDENTIAL

the form of a written narrative. This should include a copy of the completed Unanticipated Problem form, and any other diagnostic information that will assist the understanding of the event. Significant new information on ongoing unanticipated adverse effects shall be provided promptly to the study sponsor.

8.6 Reporting Procedures – Participating Investigators

As the study intervention and data collection will be conducted only at NYU, procedures for monitoring and reporting across sites are not provided.

8.7 Study Halting Rules

As this study is minimal risk, it is not anticipated that the study may be halted. However, if there is a determination of unexpected, significant, or unacceptable risk to participants, the study may be temporarily suspended or prematurely terminated as described in section 5.7.3

8.8 Safety Oversight

Following are plans for data and safety monitoring during the R00 study.

Monitoring entity. Data and safety monitoring will be overseen primarily by the PI, who will complete all monitoring procedures except those for which he will be blinded (i.e., any procedures involving group assignment). The project's biostatistician will be designated to oversee any aspects of the study for which the PI is blinded. The PI will submit any necessary reports to the IRB and NINR.

Monitoring procedures. The PI, biostatistician, and study personnel will meet quarterly to review the study protocol, participant recruitment, intervention attendance rates, achievement of intervention goals, retention rates, minimizing risk of adverse events, and data quality control. Because the PI and study personnel collecting data will be blinded to group assignment, any metrics by group assignment will be monitored by the biostatistician. **Multi-site procedures.** As the study intervention and data collection will be conducted only at NYU, procedures for monitoring across sites are not provided.

Minimizing risk. It is possible that a breach of confidentiality may occur during screening or study participation. However, every effort will be made to ensure that participant confidentiality is maintained. All investigators and key personnel will have trained in HIPAA policies and procedures and signed confidentiality agreements. Each participant will be assigned a unique ID number for data collected during the study; all study data will be de-identified so that only the ID number is associated with it. Paper linkage records for these ID numbers will be stored in the PI's office in a separate locked file cabinet, and an associated password-protected file containing the linkage records will be kept on an encrypted, password-protected server.

Each participant's blood sample will be associated with only the study ID number and stored in the Bluestone Center Biospecimen Bank (i.e., B3). De-identified data collected from study measures and blood samples will be stored on encrypted, password-protected servers indefinitely. Paper-based records will be stored in a locked file cabinet. Access to de-identified data will be restricted to the PI, co-investigators, and other study personnel, as well as approved secondary investigators. These procedures will be reviewed at quarterly meetings to ensure that data are collected in a manner to protect confidentiality of participants.

After the data retention period, de-identified data will be retained in an electronic format indefinitely for future analyses. Paper records of data obtained during the study, such as subjective measures, will be scanned or retained in secured long-term retention. Blood samples and materials derived from them will be retained until they are used completely. All protected health information, including the PI's linkage record, will be destroyed at that time to protect confidentiality.

Personnel who draw blood will apply universal precautions to reduce the risk of infection and will take steps to minimize discomfort, including application of pressure on the site following withdrawal of the needle. Participants will be observed after blood draws for any ill effects. To minimize fatigue, frustration, and anxiety that might occur during task performance, participants will be asked how they are feeling and will be offered breaks between tasks. During the MRI scan, participants will be able to squeeze a panic

CONFIDENTIAL

ball if they become claustrophobic; doing so will stop the scan so that the participant can exit the scanner.

External factors. The PI will monitor developments in the literature as the study progresses. Should it become clear that the intervention would be in any way harmful to participants, would increase risk, or would be unethical to continue, the IRB and NINR Program Officer will be notified and the study will be stopped.

Futility analysis. As this pilot randomized controlled trial is designed to provide preliminary data (e.g., effect sizes) for a future well-powered R01 application, it will not be possible to determine whether the intervention is futile for this population during the proposed study.

9 Clinical Monitoring

Clinical site monitoring may be conducted to ensure that the rights and well-being of human subjects are protected; that the reported trial data are accurate, complete, and verifiable; and that the conduct of the trial is in compliance with the currently approved protocol/amendment(s), with GCP, and with applicable regulatory requirement(s).

- Authorized representatives of the IRB and the NINR may review de-identified information, as well as participants' identifiable information, for the purposes of assuring proper conduct of the research, addressing a specific reported incident, or verifying appropriate use of funds. The Quality Assurance and Quality Improvement Division of NYU's Research and Regulatory Services may audit the study to confirm compliance. Access of any protected health information will be done in the offices of the PI in his presence. No identifiable information may be copied or taken off-site.
- The project manager (or clinical research coordinator) will audit one case per quarter, selected at random, to confirm compliance with IRB requirements, including conformance with informed consent requirements, verification of source documents, and investigator compliance.

10 Statistical Considerations

10.1 Statistical and Analytical Plans

A formal SAP will be developed for this study in consultation with the study biostatistician. Only a general overview of study statistics is included in this protocol.

10.2 Statistical Hypotheses

The sample size is too small to make inferences about relationships evaluated in the R00 study to the larger population of postmenopausal women with breast cancer. For the primary aim, effect sizes for neural markers of changes in cognitive function will be obtained. For the exploratory aims, effect sizes for correlations of exploratory outcomes to neural markers of changes in cognitive function will be calculated. The effect sizes for these relationships will be determined in the R00 study, which will inform the sample size for a well-powered study planned for future R01 applications.

10.3 Analysis Datasets

The analysis dataset will include all randomized participants (i.e., intention-to-treat).

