5.6 Total Number of Participants and Sites

Recruitment will end when 40 participants are enrolled. It is expected that approximately 40 participants will be enrolled to produce 32 evaluable participants.

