5.7 Participant Withdrawal or Termination

5.7.1 Reasons for Withdrawal or Termination

Participants are free to withdraw from participation in the study at any time on request. An investigator may terminate participation in the study if:

- Any adverse event (AE), laboratory abnormality, or other medical condition or situation occurs such that continued participation in the study would not be in the best interest of the participant.
- The participant meets an exclusion criterion (either newly developed or not previously recognized) that precludes further study participation.
- The participant becomes claustrophobic during an MRI scan.
- The participant sustains a head injury between study visits.
- The participant has an MRI-incompatible metal object implanted between assessment visits (study personnel or an MRI technologist will determine whether any new metal implants will be safe for MRI according to the procedure described in section 5.2).
- The participant fails to attend at least 70% of intervention visits.
- The participant is lost to follow-up.

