5.7.2 Handling of Participant Withdrawals or Termination

If a participant cannot be contacted for follow-up using all of the contact information collected, no further efforts will be made to contact the participant and that participant will be considered lost to follow-up. Abrupt termination of participation in the study intervention poses no safety risk to participants. As this study is minimal risk, efforts will not be made to collect safety and efficacy data after withdrawal.

If participants withdraw or are withdrawn from an intervention cycle, additional participants may be added to subsequent cycle(s) to reach recruitment targets for the number of evaluable participants.

Any data and banked specimens collected before withdrawal from the study will be retained for analysis, and no new data will be collected. If the participant requests that data and blood samples be destroyed, all paper records will be shredded, blood samples will be destroyed, and any data already processed into computer files will be removed. However, if results based on the participant's data have been submitted for publication or presentation before the request is made, the results cannot be removed from the publication or presentation.

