7.3.6 Withdrawal Visit

If a participant withdraws or is withdrawn from the study, no further study visits or procedures will be completed.

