10.6 Measures to Minimize Bias

10.6.1 Enrollment/Randomization/Masking Procedures

After written informed consent at the enrollment visit, participants will complete the baseline assessment (TP0) and be randomly assigned to the MBSR intervention group or HEP active control group in a permuted block design stratified by receipt of chemotherapy (i.e., two strata). It will not be possible to blind study participants or interventionists to group assignment. However, to reduce bias, research staff who conduct participant assessments (TP0, TP1, TP2), including the PI, will be blinded to group assignment (i.e., single blind). Participants will be reminded not to reveal their group assignment to study staff conducting assessments. The study biostatistician will have no direct contact with study participants and will not be blinded to group assignment. The biostatistician will produce and maintain the randomization codes for the permuted blocks. Randomization may only be unmasked by the biostatistician at the completion of analysis of the primary outcome, or for reporting of SAEs or UPs for which it will be essential to provide information to the PI on group assignment.

As described in section 5.7.2, participants who withdraw or are withdrawn from the study may be replaced with additional participants in the next cycle of the intervention with the intent of obtain at least 32 analyzable participants. For this study of preliminary efficacy, which is determining effect sizes, as large an analyzable sample size as possible will refine the estimates of these effect sizes.

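### Protocol 10.3 promises an intention-to-treat dataset, but withdrawal for attendance below 70% can end a woman's participation before the TP1 scan that supplies her primary change score

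*Protocol*

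**What the plan says.** On the analysis set, Protocol 10.3 reads: "The analysis dataset will include all randomized participants (i.e., intention-to-treat".

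On withdrawal, Protocol 5.7.1 opens its list with "An investigator may terminate participation in the study if" and includes this ground: "The participant fails to attend at least 70% of intervention visits". Once a woman is out, 5.7.2 says that "efforts will not be made to collect safety and efficacy data after withdrawal", and 7.3.6 says: "If a participant withdraws or is withdrawn from the study, no further study visits or procedures will be completed". Data collected before withdrawal are kept.

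On replacement, 5.7.2 says that "additional participants may be added to subsequent cycle(s) to reach recruitment targets for the number of evaluable participants", and 10.6.1 that "participants who withdraw or are withdrawn from the study may be replaced with additional participants in the next cycle". Section 5.6 sets the ceiling: "Recruitment will end when 40 participants are enrolled".

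On the outcome, Protocol 4.2.1 defines the primary endpoint as effect sizes for change in neural markers from before to after MBSR versus HEP. Section 7.1.1 schedules imaging at TP0 and TP1 only.

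On missing data, Protocol 10.4.1 and the SAP's data analysis paragraph both list nonrandom missing data among the anomalies to look for, and imputation among the remedies to use where needed. Protocol 10.4.2 refers the primary analysis to the SAP. SAP Aim 1 names neither an analysis set nor a rule for a woman with no TP1 scan.

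**The concern.** An intention-to-treat estimate describes everyone randomised, whether or not they took up the intervention. The attendance ground allows post-randomisation behaviour to decide who has a primary outcome. It ends study participation as a whole, so it removes the research assessments along with the sessions. Replacement then restores the evaluable count without recovering the missing woman's outcome.

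If the discretion is used before TP1, the women with a primary change score are selected towards good attenders, while 10.3 still calls the analysis intention-to-treat. Protocol 10.2 intends the effect sizes from this pilot to inform the sample size of a larger trial. A completer estimate read as an all-randomised one would pass any selection on to that calculation, and a confidence interval would not reveal it.

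**Working it through.** **1. The plan's own figure.** Protocol 10.5 gives 16 per group, effect size 1, two-sided alpha 0.05 and an equal-variance t-test. With 30 degrees of freedom and noncentrality 1 × √(16×16/32) = 2.828, power is 78.14%, which matches the stated 78.1%. That figure applies to 16 evaluable women per group and is not in dispute.

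**2. Can the attendance ground be met before TP1?** Protocol 6.1.1 gives eight weekly sessions and a retreat. In 7.3 these are Visits 3 to 11, and TP1 is Visit 12.
- Two visits missed: 7/9 = 77.8% with the retreat counted, 6/8 = 75.0% without. Both are above 70%.
- Three visits missed: 6/9 = 66.7%, or 5/8 = 62.5%. Both are below 70%.

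So a third missed visit settles the matter on either count, and every intervention visit precedes TP1. The protocol does not say when the 70% is assessed, so withdrawal before TP1 is possible but not certain.

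**3. What is left for the primary endpoint?** A woman withdrawn before TP1 keeps her TP0 scan (5.7.2) and has no second scan (7.3.6), hence no observed change score.

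**4. How would her absence move the estimate?** In each arm let f be the fraction of randomised women without a TP1 scan. Let g be the mean change in retained women minus the mean change that the missing women would have shown, in SD units. The all-randomised mean in an arm is the retained mean minus f × g. Therefore:

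completer difference − all-randomised difference = (f × g in MBSR) − (f × g in HEP).

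The documents give none of these four quantities. The two terms can cancel, add or reverse, so neither size nor direction is determined.

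**5. Comparison with sampling error.** At 16 per arm and d = 1:

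SE(d) = √(2/16 + 1/64) = √0.140625 = 0.375, so the 95% interval is 1 ± 1.96 × 0.375 = 1 ± 0.735, or 0.265 to 1.735.

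As a yardstick only, assume a retained-women effect of 1 SD (the value in 10.5), SD held at 1, no gap in HEP, and missing MBSR women who would have gained nothing (g = 1). The shift then equals f in MBSR. To match one standard error, f would have to be 0.375, or 7.5 of 20 women. The plan's 16 evaluable from 20 enrolled per arm allows at most 4/20 = 0.20, and only if every other scan is usable. If the missing women would have had some benefit, the shift is smaller; at full benefit it is zero. A HEP gap of opposite sign would add to it, and one of the same sign would offset it.

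**6. Would imputation by arm repair it?** If missing changes are drawn from the observed changes in the same arm, their expected mean is the retained mean m. The arm mean becomes (1 − f) × m + f × m = m, which is the completer estimate again.

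**The case against.** The strongest reply is that this is under-specification and not a contradiction. An all-randomised set with some missing outcomes is still all-randomised. Earlier data are kept, and both documents mention nonrandom missing data and imputation. That stands: a reader might infer that the plan discards low attenders or ignores missing data, and it says neither. The lack of a named method is mainly missing detail.

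A reader might also infer that falling below 70% leads automatically to removal. Section 5.7.1 is permissive, and 10.6.1 wants as large an analysable sample as possible, which argues against using the discretion freely. The PI is blinded to arm, which limits arm-dependent use if the PI decides, although attendance itself may differ between MBSR and HEP.

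A third tempting reading treats the gap between 40 enrolled and 32 evaluable as an expected withdrawal rate, and derives a large overstatement from it. Section 5.4 ties that allowance to scans spoiled by head movement or artefact. Nor does anything in the documents show that a woman who attended 5 of 8 or 6 of 9 visits would have had no benefit.

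Adherence and retention are already tracked (6.1.3, 10.4.5), and section 11 requires missing data to be explained. So most of the reporting is in place.

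What survives is narrower. When the discretion is used before TP1, the protocol itself stops collection of the primary outcome for a reason linked to adherence, and no existing text recovers it.

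**Conclusion.** The point holds, as a minor one. Sections 5.7.1, 5.7.2, 7.3.6 and 10.6.1 together permit a primary estimate weighted towards adherent completers, while 10.3 labels it intention-to-treat. This depends on an investigator using the attendance ground and doing so before TP1.

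The documents give no attendance or withdrawal rate, so neither the size nor the direction of the shift can be stated. It is probably smaller than the sampling error of about 0.375 in d. That judgement rests on 16 evaluable per arm, a true d near 1, and losses no greater than the plan's own margin. Protocol 10.2 already disclaims inference to the wider population. A reader might infer that the pilot effect will be inflated by some stated percentage, or that the next trial will be undersized by a stated number; the documents support neither figure.

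**What to change.** **Protocol.** Reconcile 5.7.1, 5.7.2, 7.3.6 and 10.6.1 with 10.3, so that low session attendance alone does not end the already scheduled TP1 and TP2 research assessments. This concerns data collection only. The safety, eligibility and loss-to-follow-up grounds, and the participant's own right to withdraw, stay as written. No view is taken on whether sessions continue.

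**SAP.** State that women are analysed in the arm to which they were randomised, whatever their attendance. Where a randomised woman still lacks a usable TP1 scan, label the observed-data effect size as complete-case. Add a sensitivity range over assumed change scores for the women without a scan, applied to each marker effect size reported under Aim 1. Do not rely on multiple imputation by arm alone, since it returns the completer estimate.

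**Cost.** A protocol amendment, a short SAP addition, and a few more of the visits and scans already scheduled. Protocol 15.3 pays $75 for TP1 and $75 for TP2, so $150 per woman retained, plus transit or parking. The scanning session takes about an hour (7.1.1) and its cost is not given. The effect estimate may also turn out smaller.

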10.4 Description of Statistical Methods

10.4.1 General Approach

See study schematic for the design of this pilot, single-center randomized controlled trial of the preliminary efficacy of an eight-week, group-based MBSR intervention versus HEP active control to improve neural markers of changes in cognitive function in postmenopausal women receiving aromatase inhibitor therapy for breast cancer. Using exploratory and descriptive analyses, the investigators will first evaluate whether any data anomalies (e.g., nonrandom missing data, erroneous outliers, multicollinearity,

CONFIDENTIAL

possible confounding) may invalidate planned analyses and then summarize data in terms of location and variability using appropriate descriptive statistics, given the variable's level of measurement and observed data distribution. As needed, appropriate remedial approaches (e.g., data transformations, imputation, nonparametric analysis methods) will be applied.

10.4.2 Analysis of the Primary Efficacy Endpoint(s)

See SAP.

10.4.3 Analysis of the Secondary Endpoint(s)

There are no secondary endpoints.

10.4.4 Safety Analyses

As this study is minimal risk, no adverse events are expected, and no formal plan for safety analyses will be developed. The procedures in section 8 will be followed for any AEs, SAEs, or UPs that occur during this study.

10.4.5 Adherence and Retention Analyses

Adherence to the intervention will be assessed using data collected in attendance records and weekly REDCap diaries of completion of homework and other mindfulness activities. These data will be described as percentage homework completed and number of minutes of mindfulness activities. Retention will be assessed as number of study assessment time points (i.e., TP0, TP1, TP2) completed.

10.4.6 Baseline Descriptive Statistics

Intervention groups will be compared on baseline characteristics, including demographic and clinical characteristics of the sample, using descriptive statistics. Inferential statistics will not be used.

10.4.7 Planned Interim Analysis

Not applicable.

10.4.8 Safety Review

As this study is minimal risk, it is not anticipated that the study may be halted. However, if there is a determination of unexpected, significant, or unacceptable risk to participants, the study may be temporarily suspended or prematurely terminated as described in section 5.7.3.

